# **Summary of Changes to the Protocol**

The previous version of this protocol (Version 1.0, 13 August 2019) was amended to create the current version (Version 2.0, 12 February 2021). The protocol history is below.

Protocol History					
Version and Date of Protocol	Comments				
Version 1.0, 13 August 2019	Original version				
Version 2.0, 12 February 2021	Added the new dose of LUM 75 mg/IVA 94 mg and adjusted the lower weight bound for the LUM 100 mg/IVA 125 mg dose.				

Key changes in the current version of the protocol are summarized below.

Change and Rationale	Affected Sections
Updated the planned dosing regimen based on PK results from Study 122 as follows:  • Added a lower dose of LUM 75 mg/IVA 94 mg for subjects	Sections 2 (Figure 2-1), 9.1 (Figure 9-1), 9.6 (Table 9-2), and 10.3 (Table 10-1)
who weigh 7 to <9 kg at Day 1 for the Rollover Subjects and at screening for LUM/IVA-naïve subjects.	
Updated the lower weight bound from 10 kg to 9 kg for the LUM 100 mg/IVA 125 mg dose	
The planned dosing regimen was also added to the study design figure.	
Added text to clarify the use of an assessment of Study 122B safety data before starting the enrollment of LUM/IVA-naïve subjects in each age group. Before initiating enrollment of LUM/IVA-naïve subjects 18 to <24 months of age, this safety assessment was performed in addition to meeting the minimum enrollment criteria in Study 122B.	Sections 2 (including Figure 2-1) and 9.1 (including Figure 9-1)
Removed footnote "c" from the "Follow-up OE" in the study design figure, as the footnote does not apply to the ophthalmologic examination.	Figure 2-1 and Figure 9-1
Added a ±30-minute window to the abbreviated physical examination performed postdose on Day 1 for the LUM/IVA-naïve subjects.	Table 3-2
Added a new section to describe the use of remote measures in extenuating circumstances, such as the COVID-19 pandemic.	Section 9.1.6; Table 3-1 and Table 3-2
Added clarification that screening sweat chloride results may be reviewed if needed to confirm eligibility.	Section 10.7
Removed the limitation that only central laboratory results for clinical laboratory assessments may be used for data analysis to allow for the use of local laboratories in extenuating circumstances, as described in new Section 9.1.6.	Section 11.4.2
Updated the analysis definitions for "Prior Medication" and "Pretreatment Adverse Event (AE)" to capture medications taken and AEs during Study 122 for the Rollover subjects.	Sections 12.3.2.3 and 12.3.5.1

Typographical and administrative changes were also made to improve the clarity of the document.

#### 2 PROTOCOL SYNOPSIS

Title

A Phase 3, Open-label, and Rollover Study to Evaluate the Long-term Safety and Tolerability of Lumacaftor/Ivacaftor Treatment in Subjects With Cystic Fibrosis Who Are Homozygous for *F508del* and 12 to <24 Months of Age at Treatment Initiation

**Brief Title** 

Long-term Safety of Lumacaftor/Ivacaftor in Subjects With Cystic Fibrosis Who Are Homozygous for *F508del* and 12 to <24 Months of Age at Treatment Initiation

### Clinical Phase and Clinical Study Type

Phase 3, safety

#### Objectives

# **Primary Objective**

To evaluate the safety and tolerability of long-term lumacaftor/ivacaftor (LUM/IVA) treatment in subjects with cystic fibrosis (CF), who are homozygous for *F508del* and 12 to <24 months of age at treatment initiation

### **Secondary Objective**

To evaluate the pharmacodynamics (PD) of long-term LUM/IVA treatment in subjects with CF, who are homozygous for *F508del* and 12 to <24 months of age at treatment initiation

#### **Endpoints**

#### **Primary Endpoint**

Safety and tolerability assessments based on adverse events (AEs), clinical laboratory (serum chemistry and hematology), standard 12-lead ECGs, vital signs, pulse oximetry, and ophthalmological examinations (OEs)

#### **Secondary Endpoint**

Absolute change from baseline in sweat chloride

### **Exploratory Endpoints**

- Absolute change from baseline in the following growth parameters:
  - o Body mass index (BMI)-for-age z-score and BMI
  - o Weight-for-age z-score and weight
  - Length/height-for-age z-score and length/height
  - o Weight-for-length z-score
- Absolute change from baseline in the following markers of pancreatic function:
  - o Fecal elastase-1 (FE-1) levels
  - o Serum immunoreactive trypsin and trypsinogen (IRT) levels
- Absolute change from baseline in fecal calprotectin, a marker of intestinal inflammation

#### **Number of Subjects**

Approximately 50 subjects

#### **Study Population**

Male and female subjects with CF, homozygous for *F508del*, and who are 12 to <24 months of age at LUM/IVA treatment initiation

**Rollover Subjects:** Subjects who completed LUM/IVA treatment and the Safety Follow-up Visit in Study VX16-809-122 Part B (Study 122B)

**LUM/IVA-naïve Subjects:** Subjects who did not participate in in Study 122B and are 12 to <24 months of age at Study 124 Day 1.

#### **Investigational Drug**

Active substance: LUM/IVA fixed-dose combination

Activity: CFTR corrector and potentiator Strength and route of administration:

- LUM 75-mg/IVA 94-mg granules for oral administration
- LUM 100-mg/IVA 125-mg granules for oral administration
- LUM 150-mg/IVA 188-mg granules for oral administration

#### **Study Duration**

[figure not shown]
**Rollover Subjects:** The total duration is up to 120 weeks (96 weeks for the Treatment Period and 24 weeks for the Follow-up OE)

**LUM/IVA-naïve Subjects:** The total duration is up to 124 weeks (up to 28 days for the Screening Period, 96 weeks for the Treatment Period, and 24 weeks for the Follow-up OE)

#### **Study Design**

This is a Phase 3, multicenter, open-label study in subjects who are 12 to <24 months of age at initiation of LUM/IVA treatment (Figure 2-1).

Figure 2-1 Study 124 Design

IVA: ivacaftor; LUM: lumacaftor; OE: ophthalmological examination; q12h: every 12 hours; wks: weeks

- LUM/IVA-naïve subjects (by age group: 18 to <24 months and 12 to <18 months) will be able to enroll in Study 124 once minimum enrollment has been met in Study 122B (n = 10 subjects in each age group), and after an assessment of safety data from Study 122B through Week 12 for ≥5 subjects in each age group.

- For Rollover Subjects, the Day 1 Visit should be the same day as the Safety Follow-up Visit in Study 122B.
- c The Safety Follow-up Visit will not be required for subjects transitioning to commercial LUM/IVA.
- d For LUM/IVA-naïve subjects, doses will be determined by weight at screening.

The subjects enrolled in this study include:

**Rollover Subjects:** Subjects who participated in Study 122B and completed the Study 122B Safety Follow-up Visit.

**LUM/IVA-naïve Subjects:** Subjects who did not participate in Study 122B and are 12 to <24 months of age at Study 124 Day 1. These subjects will enroll by age group as follows:

- Subjects who are 18 to <24 months of age can enroll in Study 124 after a
  minimum of 10 subjects (aged 18 to <24 months) have enrolled in Study 122B,
  and after an assessment of safety data from Study 122B through Week 12 for
  ≥5 subjects aged 18 to <24 months.

- Subjects who are 12 to <18 months of age can enroll in Study 124 after a minimum of 10 subjects (aged 12 to <18 months) have enrolled in Study 122B, and after an assessment of safety data from Study 122B through Week 12 for ≥5 subjects aged 12 to <18 months.

Note: Subjects who are 18 to <24 months of age will start enrolling in Study 124 before any subjects who are 12 to <18 months of age enroll as a result of the study design in Study 122, which includes sequential age cohorts.

Rollover and LUM/IVA-naïve subjects will receive LUM/IVA every 12 hours (q12h), according to a weight-based dosing regimen determined in Study 122, for up to 96 weeks.

Dose(s) and/or weight bounds may be adjusted after review of safety, tolerability, available pharmacokinetic (PK) data from Study 122, as well as any updated modeling approaches resulting from such data. Changes to study drug dose(s) and/or weight bounds will be communicated to site personnel through a memorandum entitled "Justification for Dose Selection" to ensure clarity and consistency in study conduct.

During the treatment period, doses may also be adjusted upward based on consistent weight gain; however, no downward dose adjustments will be made if a subject's weight decreases.

#### Assessments

**Safety:** AEs, clinical laboratory (serum chemistry and hematology), standard 12-lead ECGs, vital signs, pulse oximetry, physical examinations, and OEs

Pharmacodynamic: Sweat chloride

**Exploratory:** BMI, BMI-for-age z-score, weight, weight-for-age z-score, length/height, length/height-for-age z-score, weight-for-length-for-age z-score,

FE-1, IRT, and fecal calprotectin

### Statistical Analyses

No formal sample size calculations have been performed. The study will enroll approximately 50 subjects to provide data for the assessment of long-term safety in the target patient population, as requested by a regulatory agency.

Data from all safety, pharmacodynamic (PD), and exploratory endpoints will be analyzed using descriptive statistics. Raw and change from baseline values will be summarized descriptively for the continuous endpoints; number of subjects and percentages will be summarized for the categorical endpoints.

#### **IDMC Reviews**

Data will be reviewed by an independent data monitoring committee (IDMC) to ensure the safety of the subjects in the study. Procedural details of the IDMC's structure and function, frequency of meetings, and data planned for review will be included in the IDMC charter, which will be finalized before the first subject is enrolled.

Protocol VX19-809-124, Version 2.0 Page 6 of 57

#### 3 SCHEDULE OF ASSESSMENTS

Schedules of assessments are in Table 3-1 and Table 3-2.

Table 3-1 Study VX19-809-124: Rollover Subjects

	Treatment Period (Day 1 Through Week 96)						SFU Visit °	Follow-up OE	
Event/ Assessment a	Day 1 d	Day 3 (± 1 Day)	Day 15 (± 3 Days)	Weeks 12, 24, 36, 48, 60, 72, and 84 (± 7 Days)	Week 96 (± 7 Days)	As Soon As Possible After Last Dose	2 Weeks (±4 Days) After Last Dose	24 Weeks (± 14 Days ) After Last Dose	Comments
Informed consent	X								
Inclusion/exclusion criteria confirmation	X								
Telephone contact		X							Assessment of subject's status, any AEs, concomitant medications, treatments, and procedures.
Clinic visit	X		X	X	X	X	X		See Section 9.1.6 for use of remote measures in extenuating circumstances.
Length/height and weight	X		X	X	X	X	X		Measured with the subject in a dry diaper or dry underclothes. If the subject is >2 years of age and can stand unassisted and follow directions, standing height should be measured; otherwise recumbent length should be measured. (Section 11.3.1).
Vital signs	X		X	X	X	X	X		The subject should rest for at least 5 minutes, if possible, before having vital signs measured. (Section 11.4.4)
Pulse oximetry	X		X	X	X	X	X		The subject should rest for at least 5 minutes, if possible, before having pulse oximetry measured. (Section 11.4.4)

<sup>a Assessments will be performed before dosing unless noted otherwise.

b If the ETT Visit occurs ≥10 days after the last dose of LUM/IVA, SFU Visit will not be required (Section 9.1.4). Subjects who prematurely discontinue LUM/IVA treatment for AEs should be followed until the AE is considered resolved.

The SFU Visit is required for 1) subjects who complete their ETT Visit <10 days after the last dose of LUM/IVA (footnote b and Section 9.1.4); and 2) subjects who interrupt LUM/IVA treatment and complete their Week 96 Visit <10 days after the last dose of LUM/IVA; it is not required for subjects who continue onto commercially available, physician-prescribed LUM/IVA within 2 weeks (± 4 days) of completing LUM/IVA treatment at the Week 96 or ETT Visit.

d For subjects at sites activated by the time of their Study 122B SFU Visit, their Study 124 Day 1 Visit will be on the **same day** as their Study 122B SFU Visit, and any Study 124 Day 1 assessments that were specified to be performed at the Study 122B SFU Visit do not need to be repeated. If the Study 124 Day 1 Visit **does not coincide** with the subject's Study 122B SFU Visit, and if Study 124 Day 1 is ≤9 days after the Study 122B SFU Visit, the Study 124 Day 1 assessments do not need to be repeated. If Study 124 Day 1 is >9 days after the Study 122B SFU Visit, the subject will complete all Study 124 Day 1 assessments (except the OE if it was performed ≤12 weeks before the Study 124 Day 1 Visit). See Section 9.1 for details.

Protocol VX19-809-124, Version 2.0 Page 7 of 57

Table 3-1 Study VX19-809-124: Rollover Subjects

									<del>-</del>
			Treatment y 1 Through			ETT Visit b	SFU Visit °	Follow-up OE	
Event/ Assessment a	Day 1 d	Day 3 (± 1 Day)	Day 15 (± 3 Days)	Weeks 12, 24, 36, 48, 60, 72, and 84 (± 7 Days)	Week 96 (± 7 Days)	As Soon As Possible After Last Dose	2 Weeks (±4 Days) After Last Dose	24 Weeks (± 14 Days ) After Last Dose	Comments
Ophthalmological examination	X			Weeks 24, 48, 72	X	Xe		X	To be performed by a licensed ophthalmologist, preferably a pediatric ophthalmologist. May be completed $\pm$ 2 weeks of the scheduled visit. (Section 11.4.6)
Physical examination	X			X	X	X	X		Section 11.4.4
12-lead ECGs	X			Weeks 24, 48	X	X	X		The subject should rest for at least 5 minutes, if possible, before having ECGs measured. To be performed before any other procedures that may affect heart rate, such as blood draws. (Section 11.4.5)
Serum chemistry and hematology	X		X (LFTs only)	X	X	X	X		Section 11.4.2
IRT	X			X	X	X	X		Section 11.3.2.2
Sweat chloride	X			Weeks 24, 48	X	X			At each time point, 2 samples will be collected, 1 sample from each arm (left and right) (Section 11.2.1).
Fecal sample collection	X			Weeks 24, 48	X	X			May be collected during the clinic visit or by the subject's caregiver up to 48 hours before the clinic visit and brought to the clinic visit (Section 11.3.2.1).
LUM/IVA dosing	LUM/IVA q12h						Administered q12h (± 2 hours) within 30 minutes of consuming fat-containing food according to the guidelines in Section 9.6. The last dose will be the previous dose (e.g., evening dose) administered before the Week 96 Visit. See Section 9.6 for dose determination details.		
Study drug count			X	X	X	X			
Medications, treatments, and procedures review		Co	ontinuous fro	om signing of IC	F through the Sl	FU Visit			Section 9.5
AEs	Continuous from signing ICF through the S					U Visit		Ocular AEs only	Section 11.4.1

AE: adverse event; ETT: Early Termination of Treatment; ICF: informed consent form; IRT: immunoreactive trypsinogen and trypsin; IVA: ivacaftor; LFT: liver function test; LUM: lumacaftor; OE: ophthalmological examination; q12h: every 12 hours; SFU: Safety Follow-up

The OE for the ETT Visit will be conducted for all subjects who prematurely discontinue LUM/IVA dosing (for any reason) unless performed in the 12 weeks before the ETT Visit.

Protocol VX19-809-124, Version 2.0 Page 8 of 57

Table 3-2 Study VX19-809-124: LUM/IVA-naïve Subjects

	Screening	Treatment Period Screening (Day 1 Through Week 96)							ETT Visit b	SFU Visit°	Follow-up OE	
Event/Assessment a	Days -28 Through -1	Day 1	Day 3 (± 1 Day)	Day 15 (± 3 Days)	Weeks 4, 8, 12, and 16 (± 5 Days)	Week 20 (± 5 Days)	Weeks 24, 36, 48, 60, 72, and 84 (± 7 Days)	Week 96 (± 7 Days)	As Soon As Possible After Last Dose	2 Weeks (±4 Days) After Last Dose	24 Weeks (±14 Days) After Last Dose	Comments
Informed consent	X											
Inclusion/exclusion criteria confirmation	X											
Clinic visit	X	X		X	X		X	X	X	X		See Section 9.1.6 for use of remote measures in extenuating circumstances.
Telephone contact			X			X						Assessment of subject's status, any AEs, concomitant medications, treatments, and procedures.
Demographics	X											
Medical history	X											
CFTR genotype	X											Retesting is not required for subjects who have acceptable documentation of a genotype test as described in Section 11.4.2.
Length/height and weight	X	X		X	X		X	X	X	X		Measured with the subject in a dry diaper or dry underclothes. If the subject is >2 years of age and can stand unassisted and follow directions, standing height should be measured; otherwise recumbent length should be measured. (Section 11.3.1).
Vital signs	X	X		X	X		X	X	X	X		The subject should rest for at least 5 minutes, if possible, before having vital signs measured. Days 1 and 15 : Predose and 1 to 2 hours and 4 to 6 hours postdose (Section 11.4.4)
Pulse oximetry	X	X		X	X		X	X	X	X		The subject should rest for at least 5 minutes, if possible, before having pulse oximetry measured.

<sup>a All assessments may be performed pre- or postdose unless noted otherwise. When repeats of an assessment are required postdose at a given visit, the assessment will be collected only once at that visit if LUM/IVA is not administered on the day of the visit (i.e., LUM/IVA interruption or permanent LUM/IVA discontinuation).

b If the ETT Visit occurs ≥10 days after the last dose of LUM/IVA, the SFU Visit will not be required (Section 9.1.3). Subjects who prematurely discontinue LUM/IVA treatment for AEs should be followed until the AE is considered resolved.

The SFU Visit is required for 1) subjects who complete their ETT Visit <10 days after the last dose of LUM/IVA (footnote b and Section 9.1.4); and 2) subjects who interrupt LUM/IVA treatment and complete their Week 96 Visit <10 days after the last dose of LUM/IVA; it is not required for subjects who continue onto commercially available, physician-prescribed LUM/IVA within 2 weeks (± 4 days) of completing LUM/IVA treatment at the Week 96 or ETT Visit.

Protocol VX19-809-124, Version 2.0 Page 9 of 57

Table 3-2 Study VX19-809-124: LUM/IVA-naïve Subjects

	Screening	Treatment Period Screening (Day 1 Through Week 96)							ETT Visit b	SFU Visit c	Follow-up OE	
Event/Assessment a	Days -28 Through -1	Day 1	Day 3 (± 1 Day)	Day 15 (± 3 Days)	Weeks 4, 8, 12, and 16 (± 5 Days)	Week 20 (± 5 Days)	Weeks 24, 36, 48, 60, 72, and 84 (± 7 Days)	Week 96 (± 7 Days)	As Soon As Possible After Last Dose	2 Weeks (±4 Days) After Last Dose	24 Weeks (±14 Days) After Last Dose	Comments  Days 1 and 15: Predose and 1 to 2 hours and 4
Ophthalmological examination	X						Weeks 24, 48, 72	X	X d		X	to 6 hours postdose (Section 11.4.4)  To be performed by a licensed ophthalmologist, preferably a pediatric ophthalmologist. May be completed ± 2 weeks of the scheduled visit. (Section 11.4.6)
Physical examination (PE)	X	X		Abbrev	Week 12		X	X	X	X		Day 1: Full PE predose and an abbreviated PE 4 hours (±30 minutes) postdose (Section 11.4.4).
Standard 12-lead ECG	X				Weeks 4, 12		Weeks 24, 48	X	X	X		The subject should rest for at least 5 minutes, if possible, before having ECGs measured. To be performed before any other procedures that may affect heart rate, such as blood draws. (Section 11.4.5)
Serum chemistry and hematology	X	X		X (LFTs only)	X		X	X	X	X		If the screening blood draw for chemistry and hematology was collected ≤9 days before Day 1, then a Day 1 blood sample does not need to be collected.  Weeks 4 and 12: Serum chemistry and hematology are collected  Day 15, Weeks 8 and 16: LFTs only (Sections 11.4.2 and 11.4.3)
IRT	X				Weeks 4, 12		X	X	X	X		Section 11.3.2.2
Sweat chloride	X	X			Weeks 4, 12		Weeks 24, 48	X	X			Day 1 test is not required for subjects who have a valid sweat sample at screening. At each time point, 2 samples will be collected, 1 sample from each arm (left and right) (Section 11.2.1).

The OE for the ETT Visit will be conducted for all subjects who prematurely discontinue LUM/IVA dosing (for any reason) unless performed in the 12 weeks before the ETT Visit.

Protocol VX19-809-124, Version 2.0

Table 3-2 Study VX19-809-124: LUM/IVA-naïve Subjects

	Screening				Treatment (Day 1 Throug				ETT Visit b	SFU Visit c	Follow-up OE	
Event/Assessment a	Days -28 Through -1	Day 1	Day 3 (± 1 Day)	Day 15 (± 3 Days)	Weeks 4, 8, 12, and 16 (± 5 Days)	Week 20 (± 5 Days)	Weeks 24, 36, 48, 60, 72, and 84 (± 7 Days)	Week 96 (± 7 Days)	As Soon As Possible After Last Dose	2 Weeks (±4 Days) After Last Dose	24 Weeks (±14 Days) After Last Dose	Comments
Fecal sample collection	Х			• •	Weeks 4, 12		Weeks 24, 48	X	X			Sample collected before first dose of study drug may be collected either at screening OR up to 48 hours before the Day 1 Visit. All other samples may be collected during the clinic visit or by the subject's caregiver up to 48 hours before the clinic visit and brought to the clinic visit (Section 11.3.2.1).
LUM/IVA dosing			LUM/IVA			A q12h						Administered q12h (± 2 hours) within 30 minutes of consuming fat-containing food according to the guidelines in Section 9.6. The last dose will be the previous dose (e.g., evening dose) administered before the Week 96 Visit. See Section 9.6 for dose determination details.
Observation 4 hours after the first dose		X										
Study drug count				X	X		X	X	X			
Medications, treatments, and procedures review				Conti	nuous from signi	ng of ICF thr	ough the SF	U Visit				Section 9.5
AEs	A.D. 1		D) (I 1		nuous from signi				1	1	Ocular AEs only	Section 11.4.1

Abbrev: abbreviated; AE: adverse event; BMI: body mass index; CF: cystic fibrosis; CFTR: CF transmembrane conductance regulator gene; ETT: Early Termination of Treatment; ICF: informed consent form; IRT: immunoreactive trypsin and trypsinogen; IVA: ivacaftor; LFT: liver function test; LUM: lumacaftor; OE: ophthalmological examination; PE: physical examination; q12h: every 12 hours; SFU: Safety Follow-up

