### Timing of Day 1 Visit

For rollover subjects at sites activated by the Study 122B Safety Follow-up Visit, their Study 124 Day 1 Visit will be on the **same day** as their Study 122B Safety Follow-up Visit. Any Study 124 Day 1 assessments that are specified to be performed at the Study 122B Safety Follow-up Visit do not need to be repeated.

If the Study 124 Day 1 Visit **does not coincide** with the Study 122B Safety Follow-up Visit, and if Study 124 Day 1 is ≤9 days after the Study 122B Safety Follow-up Visit, the Study 124 Day 1 assessments do not need to be repeated. If Study 124 Day 1 is >9 days after the Study 122B Safety Follow-up Visit, the subject will complete all Study 124 Day 1 assessments (except the OE if it was performed ≤12 weeks before the Study 124 Day 1 Visit).

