7 STUDY DESIGN

7.1 Overall Design

This is a Phase 3, multicenter, open-label study in subjects who are 12 to <24 months of age at initiation of LUM/IVA treatment (

Figure 7-1). The study will enroll approximately 50 subjects.

Rollover Subjects

Subjects who participated in parent study VX16-809-122 Part B (Study 122B) and meet all eligibility requirements can rollover into Study 124.

For rollover subjects at sites activated by the Study 122B Safety Follow-up (SFU) Visit, their Study 124 Day 1 Visit will be on the same day as their Study 122B SFU Visit; any Study 124 Day 1 assessments that are specified to be performed at the Study 122B SFU Visit will not need to be repeated.

If the Study 124 Day 1 Visit does not coincide with the Study 122B SFU Visit, and if Study 124 Day 1 is \leq 9 days after the Study 122B SFU Visit, the Study 124 Day 1 assessments will not need to be repeated. Otherwise, if Study 124 Day 1 is >9 days after the Study 122B SFU Visit, the subject will need to complete all Study 124 Day 1 assessments (except the OE if it was performed \leq 12 weeks before the Study 124 Day 1 Visit).

Rollover subjects may receive treatment for up to 120 weeks (24 weeks in Study 122B and 96 weeks in Study 124).

LUM/IVA-naïve Subjects

[figure not shown]
Subjects who did not participate in Study 122B and are 12 to <24 months of age at Study 124 Day 1 can enroll by age group if they meet Study 124 eligibility requirements:

- Subjects who are 18 to <24 months of age can enroll in Study 124 after a minimum of 10 subjects (aged 18 to <24 months) have enrolled in Study 122B and after an assessment of safety data from Study 122B through Week 12 for ≥5 subjects aged 18 to <24 months.
- Subjects who are 12 to <18 months of age can enroll in Study 124 after a minimum of 10 subjects (aged 12 to <18 months) have enrolled in Study 122B and after an assessment of safety data from Study 122B through Week 12 for ≥5 subjects aged 12 to <18 months.

Note: Subjects aged 18 to <24 months will start enrolling in Study 124 before any subjects 12 to <18 months of age can enroll as a result of the staggered timing from the Study 122 study design, which includes sequential age cohorts.

LUM/IVA-naïve subjects may receive treatment for up to 96 weeks in Study 124.

Figure 7-1 Schematic of Study 124 Design

IVA: ivacaftor; LUM: lumacaftor; OE: ophthalmological examination; q12h: every 12 hours; wks: weeks

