10 STATISTICAL ANALYSIS

10.1 General Considerations

The Schedule of Assessments is provided in the CSP for Study 124. The precision standards for reporting safety and efficacy variables are provided in an internal Biometrics document that specifies the programming rules including the precision for derived variables.

All individual subject data will be presented in data listings based on the All Subjects Set.

Continuous variables will be summarized using the following descriptive summary statistics: number of subjects, mean, standard deviation (SD), standard error (SE), median, minimum value (min), and maximum value (max).

Categorical variables will be summarized using counts and percentages.

Baseline value will be defined as the most recent non-missing measurement (scheduled or unscheduled) collected on or before the first dose of LUM/IVA in Study 124.

For sweat chloride, values at each visit will be based on averaged measurements from left and right arms. For Rollover Subjects, baseline will be defined as the most recent non-missing measurement (scheduled or unscheduled) collected on or before the first dose of LUM/IVA in Study 124. For LUM/IVA-naïve Subjects, baseline will be defined as the average of the values at screening and the pretreatment measurement on Day 1 of Study 124. If only 1 pre-first dose measurement of sweat chloride is available, that measurement will be considered the baseline.

Change (Absolute Change) from baseline will be calculated as postbaseline value – baseline value.

Unscheduled visits will be included in the analysis as follows:

- In scheduled visit windows per specified visit windowing rules
- In the derivation of baseline measurements or last on-treatment visit
- In individual subject data listings, as appropriate
- In the derivation of max/min values and max/min change from baseline values

Visit windowing rules: Appendix defines the visit window mapping rules to derive the analysis visits for Study 124.

Repeated observations within the same visits window:

- For all PD parameters, if there are multiple measurements within a visit window, the record at the scheduled visit will be used. If there are no measurements at the scheduled visit, then 1) the record closest to the target day will be used; or 2) if there are multiple records with the same distance to the target day, the latest record will be used.

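### The 1-to-9-day start rule for Rollover children drops the same-day qualifier, and the baseline rule would then accept on-treatment Study 122B sweat chloride and fecal values

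*Protocol*

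**What the plan says.** Footnote d to Protocol Table 3-1 gives three rules for a Rollover child's Day 1, according to the gap from the Study 122B SFU Visit:

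- Same day: "any Study 124 Day 1 assessments that were specified to be performed at the Study 122B SFU Visit do not need to be repeated".
- 1 to 9 days later, as condition and waiver: "Study 124 Day 1 is ≤9 days after the Study 122B SFU Visit, the Study 124 Day 1 assessments do not need to be repeated".
- More than 9 days later: "the subject will complete all Study 124 Day 1 assessments", except an ophthalmological examination (OE) done in the preceding 12 weeks.

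Protocol 9.1 (Timing of Day 1 Visit) words the first rule as "Any Study 124 Day 1 assessments that are specified to be performed at the Study 122B Safety Follow-up Visit do not need to be repeated" and the second as "the Study 124 Day 1 assessments do not need to be repeated". SAP 7.1 also leaves the second rule unqualified: "the Study 124 Day 1 assessments will not need to be repeated".

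On the Rollover sweat chloride baseline, SAP 10.1 says: "For Rollover Subjects, baseline will be defined as the most recent non-missing measurement (scheduled or unscheduled) collected on or before the first dose of LUM/IVA". The dose meant is the first one in Study 124. The general baseline rule in Protocol 12.3.1 and SAP 10.1 works the same way and governs fecal elastase-1 (FE-1) and fecal calprotectin. Neither document sets a look-back limit, requires the child to be off drug, or confines the baseline to samples taken within Study 124.

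**The concern.** The same-day qualifier has a purpose only if some Day 1 assessments are not part of the Study 122B SFU Visit. When the next sentence drops it, a site can take the waiver to cover the whole Day 1 list, especially as the rule after 9 days calls for all of it. A sweat or fecal sample that was not taken at the Study 122B SFU Visit might then not be taken on Day 1 either. The baseline would be the last earlier Study 122B value, normally from its 24-week Treatment Period.

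For such a child, change from baseline compares on-drug with on-drug. For the others it compares on-drug with a value after a drug-free interval. These are different quantities, and which one a child contributes would depend on the gap before Day 1 or on a failed sample. Protocol 12.3.3.1 summarizes sweat chloride change, the secondary endpoint, overall on the Full Analysis Set. No planned display shows when a baseline was sampled relative to dosing, so the mixture would not be visible.

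**Working it through.** The plan states no figure on this point, so there is none to reproduce. The check is mainly textual.

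**1. The three rules side by side.** The same-day waiver is limited to what was specified at the Study 122B SFU Visit. The 1-to-9-day waiver has no limit in any of its three places. After 9 days nothing is waived except a recent OE. By contrast, Table 3-2 ties each waiver of a Day 1 sample for LUM/IVA-naïve children to an existing one: a screening blood draw no more than 9 days old, or a valid screening sweat sample.

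**2. Which assessments are exposed.** Table 3-1 marks sweat chloride, fecal sampling and the OE at Day 1 but not at Study 124's own SFU Visit. Immunoreactive trypsinogen, laboratory tests, ECG, vital signs, pulse oximetry and growth are marked at both. If the Study 122B SFU Visit was built the same way (an assumption), only the first group lacks a recent off-drug value.

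**3. What the baseline rule then does.**

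- Waiver read in full, and no sweat or fecal sample at the Study 122B SFU Visit: the rule takes the last earlier Study 122B value.
- *Repeated* read as *already done there*: the samples remain due on Day 1, and this rule produces no on-drug baseline.
- Either reading, but no valid Day 1 sweat value: SAP 10.4.1 excludes samples under 15 µL and values outside 10 to 160 mmol/L. If both arms fail and no valid SFU value exists, the rule again reaches back to treatment in Study 122B.

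**4. Drug-free interval.** Study 124's SFU window is 14 ± 4 days after the last dose. If Study 122B used the same window (assumed):

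- Same-day start: 14 − 4 = 10 to 14 + 4 = 18 days off drug.
- Start 1 to 9 days later: 10 + 1 = 11 to 18 + 9 = 27 days off drug.

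**5. Illustration of size.** Let d be the off-drug minus on-drug sweat chloride baseline, taken as positive. A child's change is Y − B with off-drug baseline B, and Y − (B − d) = (Y − B) + d with the on-drug one. If k of N children are affected, the pooled mean change moves up by k × d / N. With N = 50 from Protocol 12.1 and k and d assumed:

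| k | d = 10 | d = 20 | d = 30 |
|---|---|---|---|
| 1 | 0.2 | 0.4 | 0.6 |
| 5 | 1.0 | 2.0 | 3.0 |
| 10 | 2.0 | 4.0 | 6.0 |

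All entries are in mmol/L. For scale, the 95% CI half-width at N = 50 is 1.96 × SD / √50, which is 2.77, 4.16 and 5.54 mmol/L for assumed SDs of 10, 15 and 20.

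**6. The OE condition.** After 9 days the waiver requires an OE within 12 weeks; at 1 to 9 days no recency limit is stated. If Study 122B had an end-of-treatment OE and the same SFU window (both assumed), a start within 9 days falls at most 18 + 9 = 27 days after the last dose, inside 12 weeks.

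**The case against.** The strongest reply is that *repeated* presupposes an earlier performance: an assessment never done cannot be repeated. A full waiver would also excuse informed consent and eligibility confirmation, both marked at Day 1, which cannot be intended. This stands. A reader might infer that these children are excused from every Day 1 assessment, but the documents do not say so; that is one possible reading. The same answer largely disposes of the complaint that the same-day rule says *specified* rather than *performed*.

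Second, the content of the Study 122B SFU Visit is unknown. Study 124's SFU column is only an analogy, and an imperfect one, because the Study 122B visit is the gateway to rollover. If sweat and fecal samples were taken there, the problem shrinks to missed or invalid samples. This also stands.

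Third, same-day start is the rule for sites activated in time, and the number starting 1 to 9 days later is not given. A reader might put a share q of Rollover children on an on-drug baseline, with off-to-on change D, and compute a Rollover mean of (1 − q)D. At q = 25% and D from −10 to −30 mmol/L the bias would be 2.5 to 7.5 mmol/L. The documents support neither q nor D. That formula also assumes full return to off-drug values by Day 1, and it ignores dilution in the planned pooled summary.

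Finally, the affected endpoints are secondary and exploratory, with no hypothesis testing, and OE findings are only listed. That limits the consequence. It does not remove the missing qualifier or the absence of any off-drug condition in the baseline rule.

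**Conclusion.** The point holds in conditional form, as a cheap improvement. The 1-to-9-day rule omits the qualifier in all three places and can be read as waiving samples not taken at the Study 122B SFU Visit. The baseline rule would accept an on-treatment Study 122B value, and for sweat chloride it can do so after invalid Day 1 samples whichever way the waiver is read.

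The shift toward zero assumes that treatment lowers sweat chloride and that the effect at least partly reverses off drug. Its size cannot be derived from the documents. The 1 to 3 mmol/L for 5 of 50 children is an illustration with assumed inputs, not an estimate. The documents do not show that any child has an on-drug baseline, only that the plan neither prevents nor reveals it.

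**What to change.** 1. **Protocol Table 3-1 footnote d, Protocol 9.1 and SAP 7.1.** In both the same-day and the 1-to-9-day rule, waive only Day 1 assessments actually performed, with a result, at the Study 122B SFU Visit. The rest are done before the first Study 124 dose. Reconcile the OE recency condition between the 1-to-9-day and the later rule.
2. **SAP 10.1.** For Rollover sweat chloride, FE-1 and calprotectin, accept as baseline only values collected at or after the Study 122B SFU Visit. Flag and list any child without one, keep the raw values, leave that child out of the change summary, and report the number.

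Requiring only that the sample follow the last Study 122B dose would not be enough. In Study 124 the last dose precedes the Week 96 Visit, typically the evening before (Protocol 9.6). If Study 122B's final treatment visit ran the same way, a sample taken hours after dosing would pass.

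The cost is one wording change in three places and a short SAP rule. No procedure is added, because these assessments are already scheduled on Day 1. The downside is that a few children may lose a change-from-baseline value. If enrollment is complete, the first change can no longer alter sampling, but the second still works on its own.
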